7.2 Study Design Part I: diagnostic efficacy of Feraheme vs. Ablavar

For Part I of our study, the legal guardian(s) of all consecutive pediatric patients with suspected or known CHD referred for cardiovascular MRI will be given the option of having their child undergoing an Ablavar®-enhanced MRI or a Feraheme®-enhanced MRI, after the potential benefits and risks of both agents are clearly explained and their questions addressed. The risks and benefits of using each of these agents will be verbally discussed with the patients' legal guardians and referring cardiologists or cardiac surgeons. A copy of the written IRB-approved informed consent will be provided. Because Feraheme®-based imaging is in use at several pediatric specialty centers, including UCLA whereby Feraheme is used more frequently than GBCA-based imaging for children in our study age-group, in the current state of professional equipoise, we judge it appropriate to allow parents to participate in the choice of agent (see Section 11.1.1 for detailed justification). Those choosing to undergo an Ablavar®-enhanced MRI will be considered the "control" group while those choosing to undergo a Feraheme®-enhanced MRI will be considered enrolled in the "test" group. We plan to recruit 40 patients for test group and 40 patients for the control group with consideration of approximately 10% missing or unusable image quality. To avoid performing a study with larger-than-necessary enrollment, the Investigators will request an interim analysis at 50% enrollment for both groups. If statistical analyses, either as part of interim analyses requested by the Investigators, or after full enrollment, shows statistically significant primary endpoint comparison, we will close Part I enrollment and begin Part II enrollment using the superior agent identified in Part I. If statistical significance is not reached for the primary endpoint during interim analyses, the patient enrollment for both test and control groups will continue until full enrollment, at which time another final statistical analyses will be performed with $p < 0.025$ considered statistically significant. If statistical significance is not reached at full enrollment, we will seek advice from the DMC regarding Part II of the study, including contrast agent to be used.

See Section 11.1.1 for justification for involving the patient's parents in patient group assignment.

7.3 Study Design Part II: diagnostic efficacy of ventilator-gated MUSIC-MRI vs. self-gated MUSIC-MRI

The Part II study will commence after statistical significance of the primary endpoint of Part I is confirmed. The overall goal of Part II is to develop and validate a more advanced MUSIC-MRI pulse sequence that incorporates image acceleration and compressed sensing reconstruction techniques as well as respiratory motion self-gating methods. Our current MUSIC-MRI pulse sequence is designed for young patients (newborn to 6 years old) who undergo cardiovascular MRI under general anesthesia or sedation per our institutional standard practice. The ventilator air pressure signal is currently used as a respiratory motion gating signal in our ventilator-gated MUSIC-MRI pulse sequence. For older children with CHD who can reliably follow verbal instructions during the MRI examination, undergoing sedation or anesthesia for the purpose of MRI would not be justifiable. Therefore, a free-breathing self-gated MUSIC-MRI pulse sequence

that is capable of acquiring high-quality images of the heart and blood vessels of these patients without anesthesia/sedation or the need for a ventilator gating signal would be highly desirable. To achieve this goal, the investigators plan to first validate such a self-gated MUSIC-MRI technique against the existing ventilator-gated MUSIC-MRI technique in patients undergoing MRI under anesthesia or sedation, a similar setup as Part I. The reasons for testing the new pulse sequence in younger patients under anesthesia/sedation rather than in older patients without anesthesia are two fold: 1) This strategy provides a means for the investigators to verify the diagnostic effectiveness of the self-gated MUSIC-MRI sequence against the “gold-standard” ventilator-gated MUSIC-MRI sequence, which would not be possible in spontaneously breathing patients. 2) Even in patients under anesthesia with mechanical ventilation, potential benefits of self-gated MUSIC-MRI include shorter acquisition time (8-10 min for current MUSIC-MRI vs. approximately 4-5 min for the accelerated self-gated MUSIC-MRI) and improved respiratory motion gating, as the self-gating signal is a more direct measurement of diaphragmatic motion than the ventilator circuit air-pressure signal. Therefore, in the Part II study, we will recruit 40 patients who provide informed consent into the contrast agent group (either Feraheme® or Ablavar®) identified in Part I of the study. In each patient, the current ventilator-gated MUSIC-MRI pulse sequence and the to-be-developed self-gated MUSIC-MRI pulse sequence will be performed sequentially in a randomized order by flipping a coin. Other than the added self-gated MUSIC-MRI pulse sequence and target enrollment differences, all other aspects of study design for Part II, including patient safety monitoring and safety data recording, will be the same as Part I. The additional self-gated MUSIC-MRI pulse sequence will require approximately 5 minutes to perform. At the end of Part II study, we will perform statistical analyses specified in Section 18 to confirm the diagnostic efficacy of the self-gated MUSIC-MRI pulse sequence.

If no statistical significant difference for the primary endpoint was found in Part I, we will seek advice from the DMC regarding whether or not to start Part II of the study. If the DMC decides in favor of pursuing Part II of the study, they will also comment on which contrast agent to be used. In offering advice for the choice of agent in Part II, the Investigators will ask the DMC to take the following factors into consideration:

1. Numerical superiority of one agent in Part I, even if statistical significance cannot be reached.
2. Superiority of one agent for the secondary endpoints in Part I.
3. Differences in safety information observed during Part I, if any, and differences in safety based on the current literature at the end of Part I study, including risks of life-threatening reactions, risks to immature kidneys in the participants, potential long-term risks of gadolinium deposit in neurological tissues.

8 CRITERIA FOR EVALUATION

8.1 Part I – Comparison between Feraheme® and Ablavar®

8.1.1 Primary Endpoint

A statistically significant difference in composite image quality score for 7 important anatomical structures between Feraheme®-enhanced vs. Ablavar®-enhanced ventilator-gated MUSIC-MRI.

8.1.2 Secondary Endpoints

A statistically significant difference in image quality scores in each of the 7 important anatomical structures between Feraheme®-enhanced vs. Ablavar®-enhanced ventilator-gated MUSIC-MRI.

A statistically significant difference in sharpness measurements at the ascending aorta and the interventricular septum.

A statistically significant difference in blood-myocardium CNR measurements.

8.1.3 Safety Endpoints

- Incidence of AE for both the test group and the control group.
- Changes in vital signs recordings (hemodynamic parameters, oxygenation, and ventilator parameters) associated with Feraheme® administration
- Changes in vital signs recordings (hemodynamic parameters, oxygenation, and ventilator parameters) associated with Ablavar® administration

8.2 Part II – Comparison between Ventilator-Gated MUSIC-MRI and Self-Gated MUSIC-MRI

8.2.1 Primary Endpoint

Statistically non-inferior composite image quality score of self-gated MUSIC-MRI for 7 important anatomical structures compared to the ventilator-gated MUSIC-MRI.

8.2.2 Secondary Endpoints

1. Statistically non-inferior image quality scores for the self-gated MUSIC-MRI in each of the 7 important anatomical structures compared with the ventilator-gated MUSIC-MRI.
2. Statistically non-inferior sharpness measurements at the ascending aorta and the interventricular septum using the self-gated MUSIC-MRI compared with the ventilator-gated MUSIC-MRI.
3. A statistically non-inferior blood-myocardium CNR measurements.

8.2.3 Safety Endpoints

- Incidence of AE during and after Feraheme administration.
- Changes in vital signs recordings (hemodynamic parameters, oxygenation, and ventilator parameters) associated with contrast agent administration (Feraheme or Ablavar).

9 SUBJECT SELECTION

9.1 Study Population

Pediatric patients of all ethnicities, age newborn to 6 years, of either gender with known or suspected CHD will be recruited. This specific age population has been chosen because our preliminary experiences suggest that the PDB is greatest in the smallest and sickest children. Furthermore, all patients of ages < 6 years undergoing cardiac MR imaging are routinely examined under anesthesia with controlled ventilation independently of our study and under the direct and

continuous observation of a pediatric anesthesiologist or neonatologist. These elements minimize the relative risk of Feraheme® administration by enabling airway protection and the ability to perform non-breath-held diagnostic studies in potentially fragile patients. Our study population will include patients with any types of CHD who are clinically referred to cardiovascular MRI; however, we expect our patient recruitment to be concentrated in more complex forms of CHD, such as Tetralogy of Fallot, because these are the patients that typically have inadequate echocardiographic exams and are referred for MRI. We do not expect our study population to have eGFR<40 mL/min/1.73m², although renal insufficiency is an exclusion criteria for the Ablavar® group of Part I study.

9.2 Inclusion Criteria

1. Male or female pediatric patients (age newborn to 6 years) of all ethnicities with known or suspected CHD with insufficient echocardiographic exams and are referred for cardiovascular MRI for further evaluation of cardiac anatomy and function.
2. Written informed consent obtained from subject's legal representative/guardian(s) and ability for subject to comply with the requirements of the study.

9.3 Exclusion Criteria

1. Standard clinical contraindication to MRI, including subjects with cochlear implants and implanted cardiac devices
2. Subjects with past or current diagnosis of iron overload due to hereditary hemochromatosis or other causes (for subjects receiving Feraheme® injection only).
3. Subjects with known hypersensitivity or allergy to iron oxide particles.
4. Subjects with renal insufficiency defined as estimated glomerular filtration rate (eGFR) < 40 mL/min/1.73m² (for subjects receiving Ablavar® injection only).
5. Subjects who are critically ill at the time of MRI and for whom the period of general anesthesia and separation from the critical care nursery or intensive care unit poses added risk as deemed by referring cardiologists, cardiac surgeons or the managing radiologist (for Part II only).
6. Other medical conditions, in the judgment of the clinician investigator, that would increase the risks to the child related to participation in the study.

10 CONCURRENT MEDICATIONS

Concurrent medication is allowed as clinically necessary for the subject.

10.1 Allowed Medications and Treatments

Concurrent medication is allowed as clinically necessary for the subject.

10.2 Prohibited Medications and Treatments

None

11 STUDY TREATMENTS

11.1 Method of Assigning Subjects to Treatment Groups

Refer to Section 7.2 for patient group assignment in Part I of the study. For Part II of the study, all subjects will undergo the ventilator-gated MUSIC-MRI and self-gated MUSIC-MRI in one imaging session in a randomized order by flipping a coin.

11.1.1 Justification for Parents Participation in Patient Group Assignment

We plan to allow parents to participate in the decision about treatment assignment in Part I of this open-label, evaluator-blinded study. Feraheme-based imaging is in use at several pediatric specialty centers, including UCLA whereby Feraheme is used more frequently than GBCA-based imaging for children in our study age-group. In the current state of professional equipoise, we judge it appropriate to allow parents to participate in the choice of agent. There is no *a priori* reason to expect MRI image quality, ventricular or aortic wall definition, or the risks of anaphylaxis or other important AEs to be influenced by parental preferences; thus the generalizability of our scientific conclusions will not be diminished by allowing parents to influence the treatment assignment for their children. Recruitment of children in clinical studies is a challenging process. Based on our clinical investigative experience in the particular patient population at UCLA, many parents and/or legal guardians are more willing to participate in a study without randomization of treatment than one that required randomization of the child's treatment. We expect this route of recruitment will facilitate recruitment and successful completion of the study. In scenarios where the patient's legal guardians defer and ask the managing clinician to make 'the best choice', the decision will be based on the apparent needs of the trial at the time and the patient will be assigned the group that is under-enrolled with reference to the target enrollment. If our patient group assignment method results in a severely distorted imbalance (e.g. nearly all parents elect either Feraheme or Ablavar), the DMC will be convened and asked to advise on a corrective measure, which may include changing the patient group allocation method.

11.2 Blinding

For Part I of the trial, the image readers will be blinded to the patient's information and the contrast agent used. For Part II of the trial, the image reviewers will be blinded to the techniques used. In both cases (Part I and Part II), scores for image quality, sharpness and CNR measurements will remain blinded to the managing clinician and the Investigators and only the study statistician will be able to pair the contrast agent assignment /score (for Part I) and technique assignment /score (for Part II).

11.3 Formulation of Test and Control Products

Formulation of Test Product

Feraheme (Feraheme®) is an FDA approved drug manufactured by AMAG Pharmaceuticals for I.V. administration as an iron supplement for iron deficiency anemia in chronic kidney disease. It is an aqueous colloidal product that is formulated with mannitol. It is a black to reddish brown liquid, and is provided in single use vials containing 510 mg of elemental iron. Each mL of the sterile colloidal solution of Feraheme contains 30 mg of elemental iron and 44 mg of mannitol,

and has low bleomycin-detectable iron. The formulation is isotonic with an osmolality of 270-330 mOsm/kg. The product contains no preservatives, and has a pH of 6 to 8.

Formulation of Control Product

Ablavar® is an FDA approved MRI contrast agent for evaluation of aortoiliac occlusive disease in adults with known or suspected peripheral vascular disease. Ablavar is a sterile, nonpyrogenic, formulation of stable gadolinium diethylenetriaminepentaacetic acid (GdDTPA) chelate derivative with a diphenylcyclohexylphosphate group. Each mL of Ablavar contains 244 mg of gadofosveset trisodium (0.25 mmol), 0.268 mg of fosveset, and water for injection. It contains no preservative and the solution pH ranges between 6.5 and 8.0. Gadofosveset trisodium is chemically trisodium-{(2-(R)-[(4,4-diphenylcyclohexyl)-diethylenetriaminepentaacetato](aquo) gadolinium(III), with a molecular weight of 975.88 g/mol, and an empirical formula of C₃₃H₄₀GdN₃Na₃O₁₅P.

Packaging and Labeling

Feraheme® and Ablavar used in this study will be commercial product and will be in the commercial primary container/closure system. Investigational labels, with the required caution statement, “Caution-new drug limited by Federal Law to Investigational Use” will be used to over-label individual vials of commercial product by the UCLA pharmacy before supplying to the investigator for the clinical study.

Dosage/Dosage Regimen

Feraheme will be infused intravenously at a dose level of 4 mg of iron per kg of body weight.

Ablavar is administered by an intravenous bolus at a dose of 0.03 mmol/kg body weight over a period of time up to 30 seconds followed by a normal saline flush.

Administration Instructions

The drug will be administered by a nurse or MRI technologist who is trained on the clinical protocol and will be administered under the direction of the Principal Investigator.

11.4 Supply of Study Drug at the Site

The investigators will obtain Feraheme® and Ablavar® from the UCLA Hospital pharmacy with the investigational labels and the IND caution statement.

11.5 Storage

Feraheme will be stored at 20° to 25°C (68° to 77°F). Excursions permitted to 15° – 30°C (59° – 86°F) and ABLAVAR will be stored up to 25°C (77°F); excursions permitted to 15-30°C.

11.6 Study Drug Accountability

Both Feraheme and Ablavar used in our study will be marketed product and they will be obtained from the UCLA Medical Center pharmacy in pre-packaged sterile vials. Any unused contrast agents will be disposed of according to Standard Procedures at the imaging site.

12 STUDY PROCEDURES AND GUIDELINES

Prior to conducting any study-related activities, written informed consent and the Health Insurance Portability and Accountability Act (HIPAA) authorization must be signed and dated by the subject or subject's legal representative/guardian(s).

12.1 Clinical Assessments

Concomitant Medications

All concomitant medication and concurrent therapies will be documented at the date of study MRI. Dose, route, unit frequency of administration, and indication for administration and dates of medication will be captured.

Demographics

Demographic information (date of birth, gender, race) will be recorded at Screening.

Medical History

Relevant medical history, including history of current disease, other pertinent respiratory history, and information regarding underlying diseases will be recorded at Screening.

Physical Examination

N/A

Vital Signs / Oximetry / Ventilatory Parameters

Continuous heart rate, blood pressure, ECG, pulse oximetry, and end tidal CO_2 will be monitored for the duration of the MRI study and until the subject is recovered or returned to the Intensive Care facility, or for 30 minutes after the infusion, whichever is longer.

Adverse Events

Information regarding occurrence of acute adverse events will be captured throughout the study. Duration (start and stop dates and times), severity/grade, outcome, treatment and relation to study drug will be recorded on the case report form (CRF). Each patient will be followed up via a review of medical record at 60 days after MRI study to capture any additional AEs.

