SAFETY EVALUATIONS	
Safety Evaluations:
 
 1. Incidence of acute AE will be monitored. 2. Continuous patient monitoring and recording of vital signs (pre-, during, and at least 30 min-post contrast agent injection) will be provided by expert and specialized staff, including pediatric anesthesiologists and /or staff from the UCLA Neonatal or Pediatric Intensive Care Units. 3. Incidence of other AE up to 60 days post-MRI via a medical record review. 
Procedures to Reduce Risks of Feraheme Infusion:
 
 1. All patients will be screened for contraindications to Feraheme® administration, including a history of allergy to intravenous iron products and iron overload. 2. Performing MRI in newborns to 6 years of age under sedation and/or general anesthesia with airway protection is considered the standard of care at most institutions performing pediatric cardiac MRI for this age group. In the case of a clinically urgent or life-threatening AE during the procedure, there will already be in place full airway protection and support of respiration.

	
3. Patients will undergo continuous monitoring of heart rate, blood pressure, oxygen saturation and ECG tracing for the duration of the MRI procedure and, at a minimum, 30 min after the injection. In the case of a clinically important AE, changes in vital signs will be evident immediately and appropriate treatment initiated. Protocols are in place to deal with acute AEs related to hypersensitivity and/or anaphylaxis.
 
4. The dose of Feraheme® will be up to 4 mg /kg (approximately half the single therapy dose), diluted with saline and infused slowly per FDA guidelines.

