5.1 Benefit to Risk Assessment

Feraheme infusion is associated with risks, which include acute anaphylactoid reactions and hypotension, as well as other types of less severe adverse events such as rash, nausea and vomiting. The investigators are fully aware of the potential risks of Feraheme infusion and the following is our plan to mitigate these risks. As summarized in our Overview of Clinical Studies in Section 4.5, Feraheme® and the control contrast agent, Ablavar®, have a similar and small risk of

hypersensitivity/anaphylactoid reactions in pre-marketing clinical trials and the post-marketing data of Feraheme® safety point to a lower reported incidence of anaphylaxis than pre-marketing data. Furthermore, the elemental iron in its core is indispensable for normal biosynthesis and energy metabolism. Iron deficiency is the most widespread disorder in the world and its prevalence in children is 3-7% in the U.S. (84). It has been shown that the majority of pediatric CHD patients do not meet the recommendations for iron uptake (85). In normal neonates, body iron stores reach a nadir at about six months of age and in order to meet the demands of rapid growth must be appropriately supplemented by a diet rich in iron, such as formula. In sick neonates, body iron stores are frequently low from birth and these patients often require iron supplements (85). In these patients, it seems likely that Feraheme® may offer a nutritional iron boost, over and above its imaging applications. Therefore, for the pediatric CHD patient population in this study, who will need a high quality cardiovascular MRI exam in order to inform surgical decision-making, the Investigators feel the potential benefit for these children greatly outweighs the potential incremental risks associated with participating in this study, especially given the recent reports of gadolinium deposits in the brain tissue after repeated GBCA exposure (17-22).

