14.2 Serious Adverse Experiences (SAE)

An SAE is defined as any AE occurring at any dose that results in any of the following outcomes:

- death
- a life-threatening adverse experience
- inpatient hospitalization or prolongation of existing hospitalization
- a persistent or significant disability/incapacity
- a congenital anomaly/birth defect

Other important medical events may also be considered an SAE when, based on appropriate medical judgment, they jeopardize the subject or require intervention to prevent one of the outcomes listed.

Serious Adverse Experience Reporting

The investigators will document all SAEs that occur (whether or not related to study drug). The collection period for all SAEs will begin after informed consent is obtained and end after procedures for the study visit have been completed. In accordance with the standard operating procedures and policies of the local Institutional Review Board (IRB), the site investigator will report SAEs to the IRB.

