18.6 Safety Evaluations

AEs, SAEs, AEs resulting in premature withdrawal from the study, AEs of special interest (hypersensitivity reactions and blood pressure changes requiring intervention), and study related adverse events will be listed and summarized by contrast agent group. For the purpose of safety evaluation, the patients in both Part I and Part II who received the same contrast agent will be included in a single safety report. Due to the limited study cohort size and the small anticipated AE rates, no formal inferential statistical analyses will be performed for AEs. However, while the study is too small to expect statistical significance in sub-groups, the efficacy and safety results will be examined by standard age categories (neonates (0-to-1 month of age), infants and toddlers (1 month to 2 years of age) and children (>2 years of age)) and any clinically important differences reported.

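### AEs run to day 60 and are summarized by agent with no time window, but surgery, repeat contrast or IV iron after the MRI date is not recorded for each child

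*Combined protocol and SAP*

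**What the plan says.** **Treatment record.** Section 12.1: "All concomitant medication and concurrent therapies will be documented at the date of study MRI". For medication, dose, route, frequency, "indication for administration and dates of medication will be captured". Section 13.1 places this at item 9 of the only visit. No later collection of medication, surgery, anesthesia, contrast or iron is described. Sections 10.1 and 10.2 prohibit nothing.

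**AE record.** Section 12.1: "Each patient will be followed up via a review of medical record at 60 days after MRI study to capture any additional AEs". The synopsis (Safety Evaluations) lists acute AEs first and then, as a separate item, "Incidence of other AE up to 60 days post-MRI via a medical record review". Section 14.2, however, has serious-AE collection "begin after informed consent is obtained and end after procedures for the study visit have been completed".

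**Summary.** Section 18.6 lists and summarizes by contrast agent the AEs, serious AEs, study-related AEs and "AEs of special interest (hypersensitivity reactions and blood pressure changes requiring intervention"). It sets no start or end relative to contrast. It pools Parts I and II by agent and plans no formal inference.

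**Population and allocation.** Section 5.1 describes children "who will need a high quality cardiovascular MRI exam in order to inform surgical decision-making". In Part I the guardians choose the agent (sections 7.2 and 11.1.1).

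**The concern.** The period over which events are counted is much longer than the period over which other exposures are recorded. Section 5.1 makes surgery foreseeable in these children and also says that sick neonates often need iron supplements. A treated fall in blood pressure after an operation weeks later, or an event after a second contrast or iron exposure, would enter the same column as a reaction during the study infusion.

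Part I is not randomized, so the share of children who go on to a procedure may differ between agents. Pooling the two Parts adds a further difference: the exclusion of certain critically ill children applies to Part II only (section 9.3, item 5), so the agent carried forward gains a cohort selected differently.

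Something depends on these tables even though they are descriptive. Summarizing safety is objective 3, the DMC reviews AEs quarterly, and if Part I is not significant, section 7.3 asks the DMC to weigh safety differences seen in Part I when it advises on the agent for Part II.

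**Working it through.** The plan states no figure for this point, so there is none to reproduce. The check compares expected agent-related counts with possible background counts.

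**Agent-related events, from the documents.** Expected count = n × rate, with n = 40 per group in Part I.
- Feraheme hypotension, section 4.7.3: 33/1726 = 1.9%, so 40 × 0.019 = 0.8. Table 5 gives 2.5%, so 40 × 0.025 = 1.0. The two sources differ, and both are used as a range.
- Ablavar hypotension, Table 5: below 1%, so fewer than 40 × 0.01 = 0.4.
- Hypersensitivity or anaphylaxis, Table 5, either agent: 0.1% to 0.2%, so 0.04 to 0.08.
- Site experience, section 4.7.2: 0 of 79 children with any AE. The one-sided 95% upper bound is 1 − 0.05^(1/79) = 3.7%, or about 1.5 per 40.

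**Background blood-pressure events, by assumption.** The documents give neither the share *s* of children with surgery, repeat anesthesia, contrast or iron within 60 days, nor the chance *q* of a blood-pressure AE needing intervention given such a procedure. Assumed ranges are *s* = 10% to 80% and *q* = 10% to 50%. Background count *b* = 40 × *s* × *q*; its share of the total against 1.0 agent-related event is *b*/(*b* + 1).

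| *s* | *q* | *b* per 40 | background share |
|---|---|---|---|
| 10% | 10% | 0.4 | 29% |
| 30% | 10% | 1.2 | 55% |
| 30% | 30% | 3.6 | 78% |
| 30% | 50% | 6.0 | 86% |
| 80% | 50% | 16 | 94% |

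Background equals the agent-related count when 40 × *s* × *q* = 1, that is *s* × *q* = 2.5%, for example 25% × 10%.

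**Imbalance.** If 30% of one group and 50% of the other had a procedure (assumed), the between-agent difference is 40 × 0.20 × *q*: 0.8 events at *q* = 10% and 2.4 at *q* = 30%. That is comparable to or larger than the expected agent-related count.

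**Can the planned data separate the two?** For a child with an AE, largely yes: sections 12.1 and 14.1 record start and stop times, treatment and relation to drug. For the group, no. The AE form covers only children who had an event, so it cannot show how many in each group had surgery or re-exposure. Without that denominator the imbalance cannot be examined.

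**The case against.** The strongest reply is that the record is better than the tables suggest. Every AE carries times, severity, treatment, relation to drug and, if unrelated, the cause. Section 18.6 lists events as well as summarizing them and has a separate study-related category. The synopsis already distinguishes acute from later AEs. No inferential comparison is planned, and section 18.1 reports the agents separately. All of this stands, and it rules out three stronger readings that a reader might infer.

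- *A real acute reaction would be lost among background events.* It would not. A reaction minutes after infusion is identifiable from its recorded times and from the listing.
- *Anesthesia on the day of the MRI goes unrecorded, and hypotension at induction is counted against the agent.* That anesthesia falls on the recorded date, and section 14.1 ties AEs in time to administration of the product. Section 13.1 records vital signs and blood pressure between induction and contrast. What remains open is narrower: section 18.6 defines no start, so a blood-pressure intervention begun at induction and continuing through contrast has no stated place. The vital-sign endpoints are also untouched, since monitoring ends at recovery or return to intensive care, "or for 30 minutes after the infusion, whichever is longer".
- *Background events would exceed the signal ten- to twentyfold.* That needs, for example, 30% to 60% of children having surgery and 80% of those having a treated blood-pressure AE (40 × 0.30 × 0.8 = 9.6; 40 × 0.60 × 0.8 = 19.2). No such rates are in the documents, and section 14.1 requires an untoward occurrence, so routine postoperative support need not count.

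The reply does not close the gap. The Unrelated grade in Table 7 requires certainty, and a cause is recorded only for that grade. The higher grades appeal to a known or expected response pattern, and hypotension is listed more often for Feraheme than for Ablavar, so investigators who know the agent could grade the same late event differently. The study-related table can therefore carry part of the same problem.

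**Conclusion.** The mismatch is real and textual: events are collected to day 60 and summarized by agent without a window, while other treatment is recorded at the MRI date only. The all-cause by-agent counts and the blood-pressure count of special interest can therefore mix contrast reactions with later background events, and the planned data cannot show whether the groups differ in surgery or re-exposure.

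The size is unknown. Under the assumed ranges, background is about 0.4 to 16 events per 40 against 0.8 to 1.0 expected Feraheme hypotension events. It is the majority over most, but not all, of that range. The comparator is itself loose: the label rates are for all hypotension at the full therapeutic dose, not for hypotension requiring intervention.

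Section 14.2 adds a separate contradiction. If serious-AE collection closes at the study visit, the 60-day review does not plainly cover serious events, so even the counting period is unsettled. No sample size, power or efficacy result is affected. This is an inexpensive improvement to the safety summary, not a flaw that undermines the trial.

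**What to change.** 1. In the 60-day chart review, log for every child the date of the first cardiac surgery or catheter intervention and the date of any repeat contrast or IV iron, including an explicit entry of none.
2. In section 18.6, tabulate AEs and AEs of special interest by agent in three windows: (a) start of contrast to end of peri-procedural monitoring, as the main by-agent table; (b) from then to the first of surgery, re-exposure or day 60; (c) after that. Show the number of children with surgery or re-exposure in each group.
3. List blood-pressure interventions begun before contrast separately, as baseline.
4. State the end of window (a) once, since sections 12.1 and 13.1 describe the end of monitoring differently.
5. Reconcile the end of serious-AE collection in section 14.2 with the 60-day review in the synopsis and section 12.1.

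The cost is a few dates per child from a review already planned, slightly more abstraction time, and sparser tables.
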